8.1.2 Other Procedures

8.1.2.1 Withdrawal/Discontinuation

When a subject discontinues/withdraws prior to trial completion, all applicable activities scheduled for the final trial visit should be performed at the time of discontinuation. Any adverse events which are present at the time of discontinuation/withdrawal should be followed in accordance with the safety requirements outlined in Section 8.2 - Assessing and Recording Adverse Events.

8.1.2.1.1 Survival Follow-up

Once a subject finishes 8 or 24 cycles of treatment with pembrolizumab or experiences confirmed disease progression, the subject moves into the survival follow-up phase and should be seen in clinic as per Section 7.0 Study calendar.

8.2 Assessing and Recording Adverse Events

An adverse event is defined as any untoward medical occurrence in a patient or clinical investigation subject administered a pharmaceutical product and which does not necessarily have to have a causal relationship with this treatment. An adverse event can therefore be any unfavorable and unintended sign (including an abnormal laboratory finding, for example), symptom, or disease temporally associated with the use of a medicinal product or protocol-specified procedure, whether or not considered related to the medicinal product or protocol-specified procedure. Any worsening (i.e., any clinically significant adverse change in frequency and/or intensity) of a preexisting condition that is temporally associated with the use of the Merck's product, is also an adverse event.

Changes resulting from normal growth and development that do not vary significantly in frequency or severity from expected levels are not to be considered adverse events. Examples of this may include, but are not limited to, teething, typical crying in infants and children and onset of menses or menopause occurring at a physiologically appropriate time.

Merck product includes any pharmaceutical product, biological product, device, diagnostic agent or protocol-specified procedure, whether investigational (including placebo or active comparator medication) or marketed, manufactured by, licensed by, provided by or distributed by Merck for human use.

Adverse events may occur during the course of the use of Merck product in clinical trials or within the follow-up period specified by the protocol, or prescribed in clinical practice, from overdose (whether accidental or intentional), from abuse and from withdrawal.

Adverse events may also occur in screened subjects during any pre-allocation baseline period as a result of a protocol-specified intervention, including washout or discontinuation of usual therapy, diet, placebo treatment or a procedure.

Progression of the cancer under study is not considered an adverse event unless it is considered to be drug related by the investigator.

All adverse events will be recorded in Redcap from the time the consent form is signed through 90 days following cessation of treatment and at each examination on the Adverse Event case report forms/worksheets. The reporting timeframe for adverse events meeting any serious criteria is described in section 8.2.3.1.

8.2.1 Definition of an Overdose for This Protocol and Reporting of Overdose to the Sponsor and to Merck

For purposes of this trial, an overdose of pembrolizumab will be defined as any dose of 1000 mg or greater (≥ 5 times the indicated dose). No specific information is available on the treatment of overdose of pembrolizumab. Appropriate supportive treatment should be provided if clinically indicated. In the event of overdose, the subject should be observed closely for signs of toxicity. Appropriate supportive treatment should be provided if clinically indicated.

If an adverse event(s) is associated with (“results from”) the overdose of a Merck product, the adverse event(s) is reported as a serious adverse event, even if no other seriousness criteria are met.

If a dose of Merck’s product meeting the protocol definition of overdose is taken without any associated clinical symptoms or abnormal laboratory results, the overdose is reported as a non-serious Event of Clinical Interest (ECI), using the terminology “accidental or intentional overdose without adverse effect.”

All reports of overdose with and without an adverse event must be reported within 24 hours to the Sponsor and within 2 working days hours to Merck Global Safety. (Attn: Worldwide Product Safety; [contact])

8.2.2 Reporting of Pregnancy and Lactation to the Sponsor and to Merck

Although pregnancy and lactation are not considered adverse events, it is the responsibility of investigators or their designees to report any pregnancy or lactation in a subject (spontaneously reported to them), including the pregnancy of a male subject's female partner that occurs during the trial or within 120 days of completing the trial, or 30 days following cessation of treatment if the subject initiates new anticancer therapy, whichever is earlier. All subjects and female partners of male subjects who become pregnant must be followed to the completion/termination of the pregnancy. Pregnancy outcomes of spontaneous abortion, missed abortion, benign hydatidiform mole, blighted ovum, fetal

death, intrauterine death, miscarriage and stillbirth must be reported as serious events (Important Medical Events). If the pregnancy continues to term, the outcome (health of infant) must also be reported.

Such events must be reported within 24 hours to the Sponsor and within 2 working days to Merck Global Safety. (Attn: Worldwide Product Safety; [contact])

8.2.3 Immediate Reporting of Adverse Events to the Sponsor and to Merck

8.2.3.1 Serious Adverse Events

An adverse event or suspected adverse reaction is considered “serious” if, in the view of either the investigator or the sponsor, it results in any of the following outcomes:

- Death
- A life-threatening adverse drug experience – any adverse experience that places the patient, in the view of the initial reporter, at immediate risk of death from the adverse experience as it occurred. It does not include an adverse experience that, had it occurred in a more severe form, might have caused death.
- Inpatient hospitalization or prolongation of existing hospitalization
- A persistent or significant incapacity or substantial disruption of the ability to conduct normal life functions.
- A congenital anomaly/birth defect.

Important medical events that may not result in death, be life threatening, or require hospitalization may be considered a serious adverse drug experience when, based upon appropriate medical judgment, they may jeopardize the patient or subject and may require medical or surgical intervention to prevent one of the outcomes listed in this definition. Examples of such medical events include allergic bronchospasm requiring intensive treatment in an emergency room or at home, blood dyscrasias or convulsions that do not result in inpatient hospitalization, or the development of drug dependency or drug abuse (21 CFR 312.32).

- Important medical events as defined above, may also be considered serious adverse events. Any important medical event can and should be reported as an SAE if deemed appropriate by the Principal Investigator or the IND Sponsor, IND Office.
- All events occurring during the conduct of a protocol and meeting the definition of a SAE must be reported to the IRB in accordance with the timeframes and procedures outlined in “The University of Texas M. D. Anderson Cancer Center Institutional Review Board Policy for Investigators on Reporting Unanticipated Adverse Events for Drugs and Devices”. Unless stated otherwise in the protocol, all SAEs, expected

or unexpected, must be reported to the IND Office, regardless of attribution (within 5 working days of knowledge of the event).

- All life-threatening or fatal events, that are unexpected, and related to the study drug, must have a written report submitted within 24 hours (next working day) of knowledge of the event to the Safety Project Manager in the IND Office.
- Unless otherwise noted, the electronic SAE application (eSAE) will be utilized for safety reporting to the IND Office and MDACC IRB.
- Serious adverse events will be captured from the time of the first protocol-specific intervention, until 90 days after the last study treatment/intervention, unless the participant withdraws consent. Serious adverse events must be followed until clinical recovery is complete and laboratory tests have returned to baseline, progression of the event has stabilized, or there has been acceptable resolution of the event.
- Additionally, any serious adverse events that occur after the 30 day time period that are related to the study treatment must be reported to the IND Office. This may include the development of a secondary malignancy.

Reporting to FDA:

- Serious adverse events will be forwarded to FDA by the IND Sponsor (Safety Project Manager IND Office) according to 21 CFR 312.32.

It is the responsibility of the PI and the research team to ensure that serious adverse events are reported according to the Code of Federal Regulations, Good Clinical Practices, the protocol guidelines, the sponsor's guidelines, and Institutional Review Board policy.

Investigator Communication with Supporting Companies:

A serious adverse event is any adverse event occurring at any dose or during any use of Merck's product that:

- Results in death;
- Is life threatening;
- Results in persistent or significant disability/incapacity;
- Results in or prolongs an existing inpatient hospitalization;
- Is a congenital anomaly/birth defect;
- Is a new cancer (that is not a condition of the study);
- Is associated with an overdose;
- Is another important medical event

Refer to Table 5 for additional details regarding each of the above criteria.

Any serious adverse event, or follow up to a serious adverse event, including death due to any cause other than progression of the cancer under study that occurs to any subject from the time the consent is signed through 90 days following cessation of treatment, or the initiation of new anti-cancer therapy, whichever is earlier, whether or not related to Merck product, must be reported within 24 hours to the Sponsor and within 2 working days to Merck Global Safety.

Non-serious Events of Clinical Interest will be forwarded to Merck Global Safety and will be handled in the same manner as SAEs.

Additionally, any serious adverse event, considered by an investigator who is a qualified physician to be related to Merck product that is brought to the attention of the investigator at any time outside of the time period specified in the previous paragraph also must be reported immediately to the Sponsor and to Merck.

SAE reports and any other relevant safety information are to be forwarded to the Merck Global Safety [contact]

A copy of all reports are submitted as required by FDA, European Union (EU), Pharmaceutical and Medical Devices agency (PMDA) or other local regulators. Investigators will cross reference this submission according to local regulations to the Merck Investigational Compound Number (IND, CSA, etc.) at the time of submission. Additionally investigators will submit a copy of these reports to Merck & Co., Inc. (Attn: Worldwide Product Safety; [contact]) at the time of submission to FDA.

All subjects with serious adverse events must be followed up for outcome.

8.2.3.2 Events of Clinical Interest

Selected non-serious and serious adverse events are also known as Events of Clinical Interest (ECI) and must be recorded as such on the Adverse Event case report forms/worksheets and reported within 24 hours to the Sponsor and within 2 working days to Merck Global Safety. (Attn: Worldwide Product Safety; [contact]) Events of clinical interest for this trial include:

1. an overdose of Merck product, as defined in Section 8.2.1 - Definition of an Overdose for This Protocol and Reporting of Overdose to the Sponsor, that is not associated with clinical symptoms or abnormal laboratory results.
2. an elevated AST or ALT lab value that is greater than or equal to 3X the upper limit of normal and an elevated total bilirubin lab value that is greater than or equal to 2X the upper limit of normal and, at the same time, an alkaline phosphatase lab value that is less than 2X the upper limit of normal, as determined by way of protocol-specified laboratory testing or unscheduled laboratory testing.*

*Note: These criteria are based upon available regulatory guidance documents. The purpose of the criteria is to specify a threshold of abnormal hepatic tests that may require

an additional evaluation for an underlying etiology. The trial site guidance for assessment and follow up of these criteria can be found in the Investigator Trial File Binder (or equivalent).

1. Additional adverse events:

A separate guidance document has been provided entitled “Event of Clinical Interest Guidance Document” (previously entitled, “Event of Clinical Interest and Immune-Related Adverse Event Guidance Document”). This document can be found in the appendices and provides guidance regarding identification, evaluation and management of ECIs and irAEs.

ECIs (both non-serious and serious adverse events) identified in this guidance document from the date of first dose through 90 days following cessation of treatment, or 30 days after the initiation of a new anticancer therapy, whichever is earlier, need to be reported within 24 hours to the Sponsor and within 2 working days to Merck Global Safety. (Attn: Worldwide Product Safety; [contact]), regardless of attribution to study treatment, consistent with standard SAE reporting guidelines.

Subjects should be assessed for possible ECIs prior to each dose. Lab results should be evaluated and subjects should be asked for signs and symptoms suggestive of an immune-related event. Subjects who develop an ECI thought to be immune-related should have additional testing to rule out other etiologic causes. If lab results or symptoms indicate a possible immune-related ECI, then additional testing should be performed to rule out other etiologic causes. If no other cause is found, then it is assumed to be immune-related.

8.2.4 Evaluating Adverse Events

An investigator who is a qualified physician will evaluate all adverse events according to the NCI Common Terminology for Adverse Events (CTCAE), version 4.0. Any adverse event which changes CTCAE grade over the course of a given episode will have each change of grade recorded on the adverse event case report forms/worksheets.

All adverse events regardless of CTCAE grade must also be evaluated for seriousness.

Table 5 Evaluating Adverse Events

An investigator, who is a qualified physician, will evaluate all adverse events as to:

V4.0 CTCAE Grading	Grade 1	Mild; asymptomatic or mild symptoms; clinical or diagnostic observations only; intervention not indicated.
	Grade 2	Moderate; minimal, local or noninvasive intervention indicated; limiting age-appropriate instrumental ADL.
	Grade 3	Severe or medically significant but not immediately life-threatening; hospitalization or prolongation or hospitalization indicated; disabling; limiting self-care ADL.
	Grade 4	Life threatening consequences; urgent intervention indicated.
	Grade 5	Death related to AE
Seriousness	A serious adverse event is any adverse event occurring at any dose or during any use of Merck product that:	
	† Results in death ; or	
	† Is life threatening ; or places the subject, in the view of the investigator, at immediate risk of death from the event as it occurred (Note: This does not include an adverse event that, had it occurred in a more severe form, might have caused death.); or	
	† Results in a persistent or significant disability/incapacity (substantial disruption of one’s ability to conduct normal life functions); or	
	† Results in or prolongs an existing inpatient hospitalization (hospitalization is defined as an inpatient admission, regardless of length of stay, even if the hospitalization is a precautionary measure for continued observation. (Note: Hospitalization [including hospitalization for an elective procedure] for a preexisting condition which has not worsened does not constitute a serious adverse event.); or	
	† Is a congenital anomaly/birth defect (in offspring of subject taking the product regardless of time to diagnosis); or	
	Is a new cancer ; (that is not a condition of the study) or	
	Is an overdose (whether accidental or intentional). Any adverse event associated with an overdose is considered a serious adverse event. An overdose that is not associated with an adverse event is considered a non-serious event of clinical interest and must be reported within 24 hours.	
	Other important medical events that may not result in death, not be life threatening, or not require hospitalization may be considered a serious adverse event when, based upon appropriate medical judgment, the event may jeopardize the subject and may require medical or surgical intervention to prevent one of the outcomes listed previously (designated above by a †).	
Duration	Record the start and stop dates of the adverse event. If less than 1 day, indicate the appropriate length of time and units	
Action taken	Did the adverse event cause the Merck product to be discontinued?	
Relationship to test drug	Did the Merck product cause the adverse event? The determination of the likelihood that the Merck product caused the adverse event will be provided by an investigator who is a qualified physician. The investigator’s signed/dated initials on the source document or worksheet that supports the causality noted on the AE form, ensures that a medically qualified assessment of causality was done. This initialed document must be retained for the required regulatory time frame. The criteria below are intended as reference guidelines to assist the investigator in assessing the likelihood of a relationship between the test drug and the adverse event based upon the available information. The following components are to be used to assess the relationship between the Merck product and the AE ; the greater the correlation with the components and their respective elements (in number and/or intensity), the more likely the Merck product caused the adverse event (AE):	
	Exposure	Is there evidence that the subject was actually exposed to the Merck product such as: reliable history, acceptable compliance assessment (pill count, diary, etc.), expected pharmacologic effect, or measurement of drug/metabolite in bodily specimen?
	Time Course	Did the AE follow in a reasonable temporal sequence from administration of the Merck product? Is the time of onset of the AE compatible with a drug-induced effect (applies to trials with investigational medicinal product)?
	Likely Cause	Is the AE not reasonably explained by another etiology such as underlying disease, other drug(s)/vaccine(s), or other host or environmental factors

Relationship to Merck product (continued)	The following components are to be used to assess the relationship between the test drug and the AE: (continued)	
	Dechallenge	Was the Merck product discontinued or dose/exposure/frequency reduced? If yes, did the AE resolve or improve? If yes, this is a positive dechallenge. If no, this is a negative dechallenge. (Note: This criterion is not applicable if: (1) the AE resulted in death or permanent disability; (2) the AE resolved/improved despite continuation of the Merck product; or (3) the trial is a single-dose drug trial); or (4) Merck product(s) is/are only used one time.)
	Rechallenge	Was the subject re-exposed to the Merck product in this study? If yes, did the AE recur or worsen? If yes, this is a positive rechallenge. If no, this is a negative rechallenge. (Note: This criterion is not applicable if: (1) the initial AE resulted in death or permanent disability, or (2) the trial is a single-dose drug trial); or (3) Merck product(s) is/are used only one time). NOTE: IF A RECHALLENGE IS PLANNED FOR AN ADVERSE EVENT WHICH WAS SERIOUS AND WHICH MAY HAVE BEEN CAUSED BY THE MERCK PRODUCT, OR IF REEXPOSURE TO THE MERCK PRODUCT POSES ADDITIONAL POTENTIAL SIGNIFICANT RISK TO THE SUBJECT, THEN THE RECHALLENGE MUST BE APPROVED IN ADVANCE BY THE U.S. CLINICAL MONITOR AS PER DOSE MODIFICATION GUIDELINES IN THE PROTOCOL.
	Consistency with Trial Treatment Profile	Is the clinical/pathological presentation of the AE consistent with previous knowledge regarding the Merck product or drug class pharmacology or toxicology?
The assessment of relationship will be reported on the case report forms /worksheets by an investigator who is a qualified physician according to his/her best clinical judgment, including consideration of the above elements.		
Record one of the following	Use the following scale of criteria as guidance (not all criteria must be present to be indicative of a Merck product relationship).	
Yes, there is a reasonable possibility of Merck product relationship.	There is evidence of exposure to the Merck product. The temporal sequence of the AE onset relative to the administration of the Merck product is reasonable. The AE is more likely explained by the Merck product than by another cause.	
No, there is not a reasonable possibility Merck product relationship	Subject did not receive the Merck product OR temporal sequence of the AE onset relative to administration of the Merck product is not reasonable OR there is another obvious cause of the AE. (Also entered for a subject with overdose without an associated AE.)	

8.2.5 Sponsor Responsibility for Reporting Adverse Events

All Adverse Events will be reported to regulatory authorities, IRB and investigators in accordance with all applicable global laws and regulations.

First stage: The principal investigator will submit a response/toxicity summary to the IND Medical monitor after the first 12 subjects have completed 8 cycles

Second Stage: The principal investigator will submit a response/toxicity summary to the IND Medical monitor after additional 4 subjects have completed 8 cycles

9.0 STATISTICAL ANALYSIS PLAN

The overall response (\geq partial response) after 8 cycles of treatment is the primary endpoint. The trial will be conducted by the Simon's Minimax design and the response rate will be estimated accordingly (Simon, 1989).

It is assumed that Pembrolizumab will have a target response rate after 8 cycles of treatment of 25%. A response rate of 5% or lower is considered a failure and the new regimen will be rejected under this circumstance. When the probability of accepting a "bad" regimen (i.e. response rate $\leq 5\%$) is 0.05 and the probability of rejecting a "good" regimen (i.e. response rate $\geq 25\%$) is 0.20, Simon's Minimax design requires to enter 12 patients in the first stage. If no patient responds to the treatment, the trial will be stopped and the regimen will be declared as ineffective. If there is at least one response observed, 4 more patients will be entered in the study to reach a total of 16 patients. By the end of the study, the new regimen will be rejected if response rate is less than or equal to 2/16 and will be accepted otherwise. The operating characteristics of the trial are given as follows. When the true response rate is 5% the probability of stopping the trial early is 54%. On the other hand, if the true response rate is 0.25, the probability to stop the trial early is 3.2%. The expected sample sizes are 13.8 and 15.9 when the true response rates are 0.05 and 0.25, respectively.

If the number of responses required for moving the trial to the second stage has not been achieved, the patient enrollment will be halted until enough responses observed.

Summary statistics will be provided for continuous variables. Frequency tables will be used to summarize categorical variables. The response rate and its 95% confidence interval will be calculated. The distribution of time-to-event endpoints including progression free survival and overall survival will be estimated using the method of Kaplan and Meier.

Toxicity data will be summarized by frequency tables for all patients. For the efficacy endpoints, intent-to-treat analysis will be applied to the eligible patients. For the toxicity endpoint, per-treated analysis will be performed to include any patient who received the treatment regardless of the eligibility nor the duration or dose of the treatment received.

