2.0 TRIAL DESIGN

2.1 Trial Design

This will be an open label, single center, single arm, pilot trial based on the established dose from the phase 1 trial.

[figure not shown]
Pembrolizumab 200 mg will be administered as a single agent intravenous infusion every 3 weeks (one cycle=21 days) for up to 24 cycles.

Disease evaluation will be done at baseline and at each cycle. Patients will continue with therapy until they have progressive disease or intolerable side effects for 8 cycles initially, with an option to continue therapy beyond 8 cycles if there is continued clinical benefit without serious adverse events.

In patients who show a continued response (\geq minor response) after 8 cycles, treatment can be continued for an additional 16 cycles to a maximum of 24 cycles.

In patients who show a continued response (\geq minor response) after 8 cycles, but who choose to stop treatment after 8 cycles of therapy and then experience progressive disease within 6 months of treatment stop, treatment can be restarted for an additional 16 cycles to a maximum of 24 cycles.

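### Section 9.0 words the final Simon boundary as a rate (2/16) but limits efficacy to eligible patients; it should be stated as a count, with a rule for ineligible patients at both looks

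*Combined protocol and SAP*

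**What the plan says.** All the key text is in Section 9.0. The design is Simon's minimax, with an unacceptable response rate of 5%, a target of 25%, a false-acceptance limit of 0.05 and a false-rejection limit of 0.20.

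- **First look.** Twelve patients are entered and the trial stops if none responds. The continuation rule is a count: "If there is at least one response observed", then "4 more patients will be entered in the study to reach a total of 16 patients".
- **Final look.** The rule is worded as a rate: "the new regimen will be rejected if response rate is less than or equal to 2/16 and will be accepted otherwise".
- **Efficacy set.** "For the efficacy endpoints, intent-to-treat analysis will be applied to the eligible patients".
- **Toxicity set.** All treated patients are included whether or not they were eligible, so the plan foresees that some treated patients may be ineligible. Section 5.11 likewise allows withdrawal when enrolment proves inappropriate.

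The documents contain no replacement rule and no boundary for a denominator other than 16. Section 8.2.5 ties the two response summaries to the first 12 and the further 4 subjects, without saying what happens if one of them is ineligible.

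**The concern.** The plan allows the efficacy denominator to fall below 16, but its final rule is written for 16 only. A rate compared with 2/16 and a count of 2 or fewer agree at 16 and diverge below it. With 15 eligible patients and 2 responses, the count rule rejects the regimen and the rule as printed accepts it. The same data would then support opposite conclusions on the primary endpoint. The literal version would also break the 0.05 limit set in the same paragraph. The trial is open label (Section 2.1), so it is better to settle the reading before responses are known.

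**Working it through.** **Inputs (Section 9.0).** p0 = 0.05, p1 = 0.25, n1 = 12, n2 = 4; continue if X1 ≥ 1; final boundary 2/16.

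**Formula.** P(accept) = Σ over x ≥ 1 of P(X1 = x) × P(X2 ≥ c − x), where X1 ~ Bin(n1, p), X2 ~ Bin(n2, p) and c is the smallest number of responses that accepts. Alpha is this at p = 0.05 and power at p = 0.25.

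**1. The plan's own figures (12+4, c = 3).**
- Early stop: 0.95^12 = 0.540 and 0.75^12 = 0.032.
- Expected size: 12 + 4 × (1 − 0.540) = 13.8 and 12 + 4 × (1 − 0.032) = 15.9.
- Alpha: 0.3413 × 0.0140 + 0.0988 × 0.1855 + 0.0196 = 0.0427. The terms are X1 = 1 with X2 ≥ 2, X1 = 2 with X2 ≥ 1, and X1 ≥ 3.
- Power by the same sum at p = 0.25: 0.8013.

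Every printed figure reproduces. An exhaustive search also returns 0/12, 2/16 as the minimax design.

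**2. Responses needed under each wording.** The literal rule accepts when X/n > 2/16, that is X > n/8. At n = 16 this needs X > 2, so 3 responses. At n = 15 it needs X > 1.875, so 2; at n = 8, X > 1, so again 2. The literal rule therefore needs 3 responses at 16 and only 2 at any n from 8 to 15. The count rule always needs 3.

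**3. One exclusion.** Take the excluded patient from stage 2 (12+3) under the literal rule, c = 2. Alpha = P(X1 = 1) × P(X2 ≥ 1 of 3) + P(X1 ≥ 2) = 0.3413 × 0.1426 + 0.1184 = 0.167. With the exclusion in stage 1 (11+4), alpha = 0.3293 × 0.1855 + 0.1019 = 0.163.

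| Eligible (stage 1 + stage 2) | Literal rate: alpha | Count: alpha | Count: power |
|---|---|---|---|
| 12+4 | 0.0427 | 0.0427 | 0.8013 |
| 12+3 | 0.1670 | 0.0361 | 0.7634 |
| 11+4 | 0.1630 | 0.0359 | 0.7618 |
| 12+2 | 0.1516 | 0.0301 | 0.7189 |
| 11+3 | 0.1489 | 0.0300 | 0.7182 |
| 10+4 | 0.1446 | 0.0298 | 0.7160 |

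If a stage-1 patient later found ineligible still counts at the 12-patient look, literal alpha is 0.1634, inside the same range.

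**4. Overall alpha of the literal rule.** The figures in step 3 are conditional on an exclusion having occurred. To average over exclusions, assume each patient is ineligible independently with probability q, unrelated to response, and is removed from numerator and denominator at both looks. Overall alpha = Σ over i, j of Bin(i; 12, q) × Bin(j; 4, q) × alpha(12 − i, 4 − j).

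| Assumed q | P(at least one exclusion) = 1 − (1 − q)^16 | Overall literal alpha | Readings disagree, p = 0.05 | Readings disagree, p = 0.25 |
|---|---|---|---|---|
| 2% | 28% | 7.5% | 3.5% | 4.2% |
| 5% | 56% | 10.7% | 6.9% | 8.9% |
| 10% | 81% | 12.8% | 9.5% | 13.9% |

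The values of q are assumptions; the documents give no rate.

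**The case against.** The strongest reply is that nobody would run a Simon design on the rate reading. The design is named, the total is fixed at 16, the boundary is printed as a numerator over that total, the first-stage rule is a count, and the stated operating characteristics are those of a count. The figure 12.5% appears nowhere in the documents. This reply stands on intent: a count is almost certainly meant. It does not supply the missing rule, because the sentence says rate, the efficacy set can shrink, and nothing says what then happens at either look.

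A second reply is that the trial is a small exploratory pilot whose response rate will be reported with a 95% confidence interval, so a result of 2 of 15 would be shown with its uncertainty. That is fair and keeps the point minor. The plan nevertheless attaches formal error rates to an accept-or-reject rule.

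A third reply is that eligibility is screened before treatment at a single center, so exclusions may be rare. That may be so. At an assumed 2% per patient, 72% of trials would exclude nobody and the two wordings would never diverge.

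A reader might also infer three stronger claims that the documents do not support:

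- **That the trial's type I error is 16-17%.** That figure needs both the literal reading and an exclusion that has already happened.
- **That this is the only go/no-go rule.** The 12-patient look also stops the trial and declares the regimen ineffective, and Section 5.12 lists early-termination criteria.
- **That the decision should move to all treated patients.** The sponsor chose eligible patients explicitly. Changing that set is a trade-off and is not needed to cure this defect.

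**Conclusion.** The concern holds as a minor one. The design is correct with 16 eligible patients, and both wordings then give alpha 4.27% and power 80.1%. With any exclusion that leaves 8 to 15, the rule as printed accepts on 2 responses. Its conditional alpha is then 16.3-16.7% with one exclusion and 14.5-15.2% with two, and overall alpha is 7.5-12.8% across assumed ineligibility rates of 2-10%. The count rule never exceeds 4.3%; its cost is power, about 76% with one exclusion and 72% with two. These results assume that exclusions are unrelated to response and that excluded patients leave both numerator and denominator.

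A reader might infer from the open-label design that the reading would be picked to suit the data. Nothing in the documents shows that; the design only makes it sensible to fix the reading in advance.

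**What to change.** In Section 9.0, keep the eligible set and replace the rate with a count, for example: *At the final look the regimen is rejected if 2 or fewer eligible patients respond and accepted if 3 or more respond, whatever the number of eligible patients up to 16.* Add one sentence on how a patient found ineligible is handled at the 12-patient look and at the final look. It should say whether a response in such a patient counts, and whether the first-stage rule then rests on fewer than 12 or the patient is replaced.

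The cost is one or two sentences. Without replacement, sample size and procedures do not change; replacing ineligible patients would mean entering more than 16. The edit protects alpha but does not restore power, which falls below the stated 80% once any patient is excluded without replacement. The section should say so.
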